C.4.1.2. Exclusion Criteria. Subjects will not meet criteria for Schizotypal Personality Disorder (SPD). SPD is excluded to avoid a possible confound from the restricted affect that characterizes SPD. BPD subjects will not meet DSM-5 criteria for past or present bipolar I disorder, schizophrenia, schizoaffective disorder, substance dependence, organic mental syndromes, head trauma, CNS neurological disease, or seizure disorder. Subjects currently meeting DSM-5 criteria for PTSD will be excluded, unless they are in remission or not currently experiencing symptoms. Subjects currently meeting criteria for major depressive disorder will also be excluded (except as described above). However, since depression is commonly associated with BPD (Koenigsberg et al., 1999), too stringent a depression exclusion criteria would yield a clinically atypical BPD sample. For this reason, BPD patients with Axis I depressive disorders other than major depression and those with a past history of major depression, will not be excluded. Suicidal subjects will not be excluded, unless referral to a higher level of care is deemed clinically necessary by the evaluating clinician. Subjects must not have met criteria for a substance use disorder for 6 months prior to entry into the study. All subjects must be free of significant medical illness. They may not have a pacemaker, surgical clips, any metallic implants, or shrapnel fragments that would contraindicate MRI scanning. Pregnant women will be excluded.

C.4.2. Sample Size, Recruitment and Assessment

C.4.2.1 Sample Size. R61 Phase: (see Power Analysis C.4.5.1). 49 BPD subjects will be recruited each for the training and control groups to acquire 39 subjects in each group allowing for a 20% loss for drop out and fMRI movement artifact. R33 Phase: 65 BPD subjects will be recruited each for the training and control groups to obtain 51 subjects per group, allowing for 20% loss.

C.4.2.2 Recruitment:
Subjects will be recruited
by newspaper, radio,
and social media
advertisements and by
referral from the
psychiatry outpatient
department at Mount
Sinai Medical Center, the
Center for the Intensive
Treatment of Personality
Disorders at Mount Sinai
West, and the Bronx VA
Medical Center. We are
confident that we can
meet recruitment goals
for both R61 and R33 as
our Mood and
Personality Disorders
Research Program at
Mount Sinai, which has
been engaged in
neurobiological research
studies of BPD for over

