C.5.1 R61 Phase. Analyses for Aims R61-2a and R61-2b are described in image analysis (C.6.4, below). Aim R61-2c: Data will be checked for normality and appropriate transformations will be applied to normalize them. Data analysis will primarily use linear mixed models, incorporating fixed effects for Training Group (CRD and ES), Session, and Trial Type (Look Neutral, Look Negative, and Regulate Negative), and their interactions, as well as a random effect consisting of an intercept for each participant. We will examine additional models that incorporate and estimate random-effects slope variance across participants on the time effect (i.e., Session). Outcome variables will be repeated measures in self-reported negative affect and reappraisal success (defined as the Look Negative minus Regulate Negative behavioral valence rating at each Session). Although we do not anticipate large differences in

baseline characteristics between the groups, given that the trial is randomized, we will include variables that are strongly unbalanced at baseline (p< 0.01) as covariates in our models.

C.5.2 R33 Phase. Aim R33-1: The primary outcome measure is the Zanarini total score (ZTS;[57]). We compare the change in ZTS from baseline to end of treatment (EOT) between groups by mixed effect models with group, time and their interaction as fixed effects. A similar analysis will be carried out for the additional outcome measures specified in C.3.3. (Table 1), using the Holm's procedure for correction for multiple comparisons. Aim R33-2: The analysis will be as for R61 Aims R61-2 a,b and c. Aim R33-3: The analysis is described in imaging analysis section C.6.3. Aim R33-4: As above, we will use linear mixed models to examine change in ZTS as the outcome variable. Bonferroni corrections will be applied for multiple clinical outcome measures. P-values throughout will be 0.05, two tailed. All analyses will be conducted according to the intent-to-treat principle for both the R61 and the R33 phase. As a sensitivity analysis we will also consider models that adjust for the number of sessions actually received. Missing data will be assumed as MAR. Under this assumption, a mixed model approach that uses all available information will yield reasonable estimates of the effect sizes.

C.6. Image Acquisition and Analysis

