C.6.2 Image Preprocessing. The 4 time series of T2*-weighted images acquired during the emotion regulation task at each time point will be separately motion corrected and coregistered to the respective MP-RAGE image. Time series with more than 1 voxel of motion (≥ 2.1 mm) or rotation (≥ 2.1°) will be discarded. Next, to optimize the images for cross-session contrasts of treatment effects, the week 2, week 4, and week 6 time series will be separately coregistered to the week 0 series (R61) and the EOT time series will be co-registered to the baseline series (R33). The coregistered sets of time series will then be jointly normalized to the Montreal Neurological Institute template and smoothed with a 6-mm Gaussian kernel. C.6.3 First-Level Modeling of Individual Treatment Effects. General linear models (GLM) will be conducted individually for each participant to jointly fit the week 0, 2, 4, and 6 time series (R61) or the baseline and EOT time series (R33). Beta weights will be fit to regressors for the 3 trial events of interest (Look Neutral, Look Negative, and Regulate Negative) and 2 trial events of no interest (Instruction, Rating), as well as 6 motion parameters [62], convolved with the hemodynamic response function [63]. Appropriate linear contrasts will be applied to the beta weights for Regulate Negative events minus Look Negative events in week 2, week 4, and week 6 (all versus week 0) in the R61 phase and EOT versus baseline in the R33 phase. The resultant contrast maps represent the effects of treatment on whole-brain activation for emotion regulation. To estimate the effect of treatment specifically on PINES network activation, the contrast maps will be scaled by the PINES weight map (downloaded from Chang PLoSBiology PINES) by calculating the voxel-wise dot product of the two maps. The effect of treatment on neural activation in emotion-specific regions (e.g., amygdala) and topdown control regions (e.g., dIPFC) will be modeled using the unweighted contrast maps together with masks derived from the "aal.002" atlas for automatic anatomic labeling [64] and the metaanalysis conducted by Buhle et. al. [48].

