C.6.4 Second-Level Analysis of Group Differences in Treatment Effects. Randomeffects GLM will use two-sample t-tests to compare the neural effects of reappraisal-bydistancing (CRD) and control training. The 3 contrast maps (weeks 2, 4, 6) for each participant in the R61 phase and the EOT versus baseline contrast map for each participant in the R33 phase will be entered as dependent variables in separate GLM in which gender, age, education level, and pre-treatment ALS score will serve as covariates. The speculative purpose of the R61/R33 mechanism justifies setting the alpha level at a relatively liberal value of p<0.05 and a cluster threshold of 50 contiguous voxels. The hypothesized effects of treatment would be supported by findings of significant reductions in PINES activation for emotion regulation in the CRD training compared to the CD control training condition at either weeks 2, 4, or 6 or at EOT. The decision to proceed to the R33 phase is based on finding a statistically significant difference in reduction in PINES activation between the CRD and control conditions. EOT versus baseline contrast maps for all participants in the R33 phase will be entered into a GLM that will use multiple regression to test for differential changes in activation in the regions of interest associated with improvement on clinical outcome variables for distancing training compared to the control condition. The 3 regressors will include: (1) % change in clinical outcome variable; (2) dichotomous treatment type variable; and (3) an interaction term (i.e., product), which identifies activation change related to differential response to the two treatments. The regressors will be centered on zero.

C.7. Power Analyses:

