R61 Phase: The primary outcome measures are decreases from baseline in PINES network activity in the REGULATE (vs. LOOK) conditions in CRD training vs. the CD condition at the 2-, 4-, and 6-week treatment doses. A significant effect at any dose will meet milestone criteria. In our previous work (see C. 1.3.3 above), we obtained a strong effect size of d = 0.73 for 5 days of training. We will, however, power the current study at a more moderate power of d = $\underline{.65}$ to increase our detection sensitivity. We can achieve this at α = 0.05 (\underline{two} — tailed), power = 0.80 with an n = $\underline{39}$ per group (G-Power 3.1). **R33 Phase:** The primary outcome measure for the R33 is the effect of CRD-training upon BPD relevant symptoms, assessed by the Zanarini Rating Scale (see C.4.2.3). A meta-analysis of randomized controlled clinical trials of psychotherapy for BPD reported an effect size of 0.56 for seven stand-alone trials employing BPD-relevant outcomes [65]. Powering to detect an effect size of 0. $\underline{56}$ with a power of 0.80 at \underline{two} -tailed α = 0.05 requires 51 subjects per group.

C.8 Potential Study Complications and Alternative Outcomes

Recruitment Shortfall: We will closely monitor the rate of subject recruitment. If the rate at the 3- or 6-month time points, extrapolated, suggests that the recruitment goals will not be met, we will implement the measures described in section 2.5 (Recruitment and Retention Plan), including, modifying exclusion criteria to allow entry of subjects currently on psychotropic medication and /or in psychotherapy, provided that dose or session frequency has not changed in the prior 2 months. Treatment will be recorded and entered as a covariate in analyses. R61: Alternative Outcomes: It is possible that, contrary to our hypothesis, CRD-, will not be superior to CD-training in reducing PINES activity. While such a finding would not meet milestone criteria, this observation would motivate future research to further explore the active features of CD (as well as nonspecific factors) in the treatment of BPD.

D. Resource Sharing Plan

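### The R61 milestone is tested week by week with t-tests and no stated handling of missing scans, unreconciled with the intent-to-treat and MAR statements in C.5.2

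*Combined protocol and SAP*

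**What the plan says.** **The decision.** C.6.4 states: "The decision to proceed to the R33 phase is based on finding a statistically significant difference in reduction in PINES activation" between CRD and control. C.7 adds: "A significant effect at any dose will meet milestone criteria".

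**The test.** In C.6.4 the second-level model "will use two-sample t-tests to compare the neural effects" of the two trainings. The week 2, 4 and 6 maps "will be entered as dependent variables in separate GLM in which gender, age, education level, and pre-treatment ALS score will serve as covariates". C.6.3 builds each map from a contrast of "Regulate Negative events minus Look Negative events in week 2, week 4, and week 6 (all versus week 0) in the R61 phase". C.6.2 discards any time series with motion or rotation of 2.1 mm or 2.1° and above. Section C.6 does not say how a participant with a missing or rejected scan enters the group test.

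**The principle.** C.5.2 states: "All analyses will be conducted according to the intent-to-treat principle for both the R61 and the R33 phase". It then takes missing data as MAR and says that "a mixed model approach that uses all available information will yield reasonable estimates of the effect sizes". This text closes section C.5, on behavioural data. C.5.1 sends the imaging aims R61-2a and R61-2b to C.6.4.

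**The expected loss.** C.4.2.1 recruits 49 per group to obtain 39, "allowing for a 20% loss for drop out and fMRI movement artifact".

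**The concern.** The R61 primary outcome is change in PINES activity, and its test is the gate to R33. The only missing-data method in the plan is a mixed model, and C.6.4 does not use one for this outcome. A per-week t-test on change scores takes nothing from a participant who has usable scans at weeks 0, 2 and 4 but not at week 6. It is unbiased only if loss does not depend on earlier response, or shifts both arms equally. That is a stronger condition than the MAR assumption in C.5.2.

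At stake is a go/no-go result that could be pushed either way by who stays in the study. Power is also lost, because scans already paid for are ignored. C.2.4 defends the single six-week cohort partly by its gain in power and in within-subject comparison, and this test gives up some of that gain.

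**Working it through.** **1. The plan's own sample size.** Inputs from C.7: d = 0.65, two-sided α = 0.05, power 0.80. For a two-sample t-test the noncentrality is d√(n/2) on 2n − 2 degrees of freedom. At n = 39 this is 0.65 × √19.5 = 2.87 on 76 df, and power is 0.809. At n = 38 power is 0.799. So 39 per group reproduces. Allowing for loss, 39/0.80 = 48.75, rounded up to 49, which matches C.4.2.1. The test is therefore sized on the roughly 80% with usable data, not on the 49 randomised.

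**2. Who enters each week's test.** Each map needs a week 0 scan and that week's scan (C.6.3), rejected series are discarded (C.6.2), and the power calculation uses 39 of 49. The natural reading is that each test uses whoever has that pair of scans. This is an inference; the plan does not say it. The separate GLMs may be separate by week or by phase, but neither reading gives a longitudinal group model. The joint fit of all weeks in C.6.3 is within one participant and does not recover missing scans.

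**3. Where bias comes from.** Let Y2 and Y6 be changes at weeks 2 and 6 with unit variance and correlation ρ. If loss after week 2 depends only on Y2 (MAR), then within an arm

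E[Y6 | observed] − E[Y6] = ρ × (E[Y2 | observed] − E[Y2]).

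The t-test bias is ρ times the difference between arms in that week 2 shift. It is zero if loss is random, or if the shift is equal in both arms. The likelihood estimate adds b × (mean Y2 of all − mean Y2 of those observed) in each arm, where b is the pooled regression slope of Y6 on Y2. This removes the bias.

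**4. Size.** From the documents: 49 per arm, 20% loss, d = 0.65, α = 0.05. Assumed: all loss is dropout after week 2, ρ is 0.5 or 0.7, the log-odds of leaving rise by 1 or 2 per SD of poorer week 2 response, and there are no covariates. There were 20,000 simulated trials per row. Positive bias favours CRD. Rejection for the likelihood estimate uses its simulated standard error.

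| Scenario at week 6 | ρ | log-odds | t-test bias (SD) | t-test rejects | likelihood bias (SD) | likelihood rejects |
|---|---|---|---|---|---|---|
| No effect, poor responders leave CRD only | 0.5 | 1 | +0.087 | 6.7% | 0.000 | 5.1% |
| same | 0.5 | 2 | +0.130 | 8.6% | −0.001 | 4.9% |
| same | 0.7 | 1 | +0.119 | 8.4% | −0.001 | 5.0% |
| same | 0.7 | 2 | +0.182 | 12.8% | −0.001 | 5.0% |
| d = 0.65, random loss | 0.5 | – | 0.000 | 80.6% | +0.001 | 83.6% |
| same | 0.7 | – | +0.001 | 81.1% | +0.001 | 85.4% |
| d = 0.65, same rule in both arms, week 2 effect 0.43 | 0.5 | 1 | −0.025 | 78.9% | −0.002 | 83.7% |
| same | 0.7 | 2 | −0.072 | 76.6% | 0.000 | 85.6% |

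Allowing for simulation error and small differences in set-up, I round the first block to 0.09 to 0.19 SD and 7% to 14%. I round the shared-rule bias to 0.03 to 0.08 SD against CRD. If the full 0.65 is already present at week 2, the shared-rule bias is larger, at 0.04 to 0.11 SD. With no true effect and the same rule in both arms, bias is about zero and type I error about 5%.

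**The case against.** **The plan never promised mixed models for imaging.** This stands. In C.5.2 the reach to all analyses attaches to intent-to-treat only. The mixed-model sentence sits in the behavioural section, and C.5.1 routes the imaging aims elsewhere. A reader might infer that C.6.4 breaks a stated commitment to mixed models; the text does not support that. What remains is a gap: the intent-to-treat statement covers the R61 primary outcome, and no section says how missing scans of that outcome are handled.

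**The inflated error needs loss that depends on response differently by arm.** This also stands. Pictures and contact time are matched (C.2.4, C.2.6.2), and the retention measures apply to everyone (C.4.4). Section F allows that symptoms may worsen in training, but for both conditions. Differential loss is possible, and the documents do not predict it.

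**The modelled loss is not the planned loss.** Partly right. The 20% includes movement artefact, which can be intermittent. C.6.2 rejects single time series, of which there are four per session, so one rejected run need not cost a scan.

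**The figures are not the milestone's error rate.** Correct. A reader might take 7% to 14% as the chance of a false go. It refers to week 6 alone, whereas any of three weeks can meet the milestone, and week 2 probably loses fewest scans.

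**The effect on dose choice is uncertain.** Also correct. C.2.2 and C.2.6 describe selection from R61 results, while C.2.4 and C.4.3.1 already state six weeks for R33. Those sections must be reconciled in their own right.

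None of this gives the per-week t-test an advantage. The likelihood estimate was essentially unbiased in every MAR scenario run, and more powerful under random loss.

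**Conclusion.** The point holds as an unreconciled gap between C.5.2 and C.6.4 on the R61 primary outcome, with a better analysis available at almost no cost. The milestone test is not protected under the plan's own MAR assumption.

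Week 6 bias is about 0.09 to 0.19 SD, with type I error about 7% to 14%, if poor responders leave CRD only. Bias runs against CRD by about 0.03 to 0.08 SD at d = 0.65 if both arms share the loss rule and the week 2 effect is about two-thirds of the final one. It is nil under random loss. Under random loss the mixed-model approach gains about 3 to 4 points of power at week 6.

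These sizes rest on assumed correlations and loss mechanisms that the documents do not give. The documents do not support reading this as a known bias in favour of CRD. The four baseline covariates would remove only the part of the loss relation that they explain.

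**What to change.** 1. In C.6.4, extract one Regulate-minus-Look PINES score per scan at weeks 0, 2, 4 and 6. The dot product is linear, so the difference between two such scores equals the score of the change map.
2. For the milestone, fit one linear mixed model to these scores with group, week, group × week, unstructured covariance (4 × 5/2 = 10 parameters) and the four covariates already named. Include every randomised participant with any usable scan.
3. Read the CRD minus CD differences in change from week 0 at weeks 2, 4 and 6 from this model. Keep the t-tests for the voxel-wise maps.
4. Use the same likelihood approach for baseline and EOT PINES in R33.
5. State how rejected runs and scans are treated, and report scan loss by arm, week and cause, including participants with no usable scan.
6. Say plainly that the model does not cure loss that depends on unseen response (MNAR), and add a sensitivity analysis for it.

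The cost is wording in C.6.4, a cross-reference from C.5.2 and a few lines of code. Sample size, scans and visits do not change.

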Overall, cognitive reappraisal has been demonstrated to be a particularly effective strategy. Individuals who use cognitive reappraisal, in comparison to other regulation strategies, show a better sense of well-being, enhanced social relationships, better memory and less cardiovascular sympathetic arousal [25, 29, 30]. In particular, the distancing tactic of CR had the largest effect size (d=.45) [31] of various emotion regulation strategies examined [22]. Further, a direct comparison of distancing and reinterpretation CR tactics has shown that longitudinal training in distancing uniquely yields significant reductions in perceived stress in daily life [26]. We have previously shown that BPD patients show impairments in cognitive reappraisal associated with anomalous neural activation when attempting to reappraise-by-distancing (see C.1.3.1. for previous results). They fail to engage the top-down cortical regions typically employed by healthy subjects (HCs) and do not downregulate amygdala activity as HCs do [32]. This observation motivated us to explore whether BPD patients could be trained to enhance the effectiveness of cognitive reappraisal-by-distancing, the central aim of our recently completed NIMH funded study (R01 MH077813). In this study, we demonstrated that with 5 sessions of focused cognitive reappraisal-by-distancing (CRD) training, BPD patients were able, when reappraising negative pictures (vs. just looking), to reduce activity (p=0.03, one-tailed) in the picture induced negative emotion signature (PINES) network, a whole-brain pattern derived through machine learning that is sensitive and specific to picture induced negative emotion [33]. PINES activation increases monotonically with subjectively reported levels of negative emotion. This network is more sensitive and specific for emotional reactions to negative pictures than other regions associated with negative emotion alone, such as the amygdala, insula, salience network and default mode network. In addition to the decreased PINES response, we found that, behaviorally, subjects showed a decrease in ratings of negative valence after training (p <0.03).

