circuits implicated in reappraisal. BPD subjects (N=19), and healthy volunteers (HC; N=18) performed a cognitive reappraisal-by-distancing task 5 times: at baseline while fMRI images were acquired, then for three additional training sessions, and again on a 5th session when fMRI images were once again acquired. The sessions were separated by 2-3 days each. The reappraisal-by-distancing task, similar to the task to be employed in the present proposal (see more detailed description below), comprised 3 conditions presented in random order, in which subjects received the instruction either: 1) to apply reappraisal-by-distancing when viewing negative emotional pictures (Reappraise-Negative Condition; RNeg), 2) to simply look at a negative picture, self-monitoring feelings induced by the picture (Look-Negative Condition; LNeg), or 3) to simply look at a neutral picture, self-monitoring the feelings present (Look-Neural

Condition; LNeu). Following each picture presentation, the subject was prompted to rate how negative they were feeling on a scale from 1 (least negative) to 5 (most negative), after they carried out the instruction. A total of 90 trials (30 each condition) were presented each day, with different pictures each day. We selected pictures that involved interpersonal interactions. The *reappraisal training* carried out each day consisted of two parts and followed a standardized script. First the subjects read a brief description of the distancing strategy written in lay language and were encouraged to discuss their understanding of the strategy and ask questions of the

[figure not shown]

experimenter. Subjects practiced distancing with several pictures, describing their thought process to the experimenter and receiving feedback to help shape their performance. Second,

they performed the distancing tactic on 20 practice pictures before beginning the 3-condition reappraise by distancing task described above.

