Analysis of the behavioral data demonstrated a decrease from baseline to session 5 in negative valence ratings in the BPD group in the Look-Negative as well as the Reappraise-Negative condition, suggesting the possibility that the effect of reappraisal training carried over to the Look condition, even without conscious intention. This observation is particularly encouraging in terms of *training generalizability*, since it suggests that training in distancing may facilitate its *automatic engagement*, without need for deliberate intent. We found (see fig 7) that the total negative valence ratings for RNeg and LNeg showed a significant decrease post-training (p< 0.05, twotailed). In terms of neural activity, we hypothesized that effective reappraisal of negative affective pictures would result in a downregulation of activity in a network known to

represent a sensitive and specific neural signature responsive to viewing aversive negative pictures, the PINES network [33]. We found that, as expected, after reappraisal training BPD patents showed decreased PINES activity when reappraising (vs. looking) relative to pretraining, with a large effect size (d=0.73, p<0.03, one-tailed; see Fig. 8). Thus, we found that with 5-days of reappraisal-by-distancing training BPD patients were able to significantly improve their ability to downregulate activity in the brain

network activated by negative emotion, and behaviorally to reduce how negatively they rated aversive pictures.

C.2. Overall Design

The present proposal follows the R61/R33 experimental medicine model to refine and test a proposed clinical intervention for BPD patients, training in reappraisal-by-distancing, in terms of its ability to influence hypothesized neural and behavioral targets and, once that is established, to demonstrate its ability improve clinically relevant outcome measures.

C.2.1. R61 Phase. Specifically, in the R61 phase we will determine whether reappraisal training will have an effect upon hypothesized proximal neural targets (see below) and behavioral measures (assessed by means of our imaging task; **C.2.6.**), further develop our treatment manual and will test 3 doses of the treatment with BPD patients -- treatment delivered 2 times a week for 2, 4 and 6-weeks. The reappraise-treatment condition will be contrasted with a control condition (**C.2.7.2**). Therapist's adherence to the manual will be assessed.

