C.2.2. Milestones to Proceed to R33 Phase and Optimal Dose Determination. We have selected milestones for the present study, cognizant of the need to achieve a balance: criteria sufficiently stringent to insure that a target-based treatment is genuine on the one hand, yet which also guards against discarding an important treatment advance on the other. Ultimately, the goal of reappraisal training is to improve subject's ability to reduce their negative emotional reactions to aversive cues, which we expect (and will test in the R33 phase) to improve their ability to handle stress and to reduce the clinical symptoms of BPD. We hypothesize that such clinical improvements would be associated with an improved ability to downregulate activity in the negative emotion responsive brain regions. As described above, with training, we expect to see an improvement in downregulation of the PINES network response to negative pictures. Our prior studies (see C.1.3.3) suggest that the neuroimaging measures are more sensitive to change than the behavioral measures – the effect size of 5days of training on PINES activity was large (d =0.73), while the effect on behavioral ratings of negative valence, though significant, was small (d=0.15). We did not see an increase in activity of the top-down control regions with training in the BPD, although after training the BPD's maintained activity in these regions at baseline levels in contrast to HC's whose activity decreased, possibly because of increased efficiency. Thus it is possible that, unlike HC's, BPD's do not have the ability to upregulate these regions, but rather bring about decreased PINES activity through enhancement of "bottom-up" regulatory processes. These guestions require further exploration.

The milestone to proceed to the R33 phase is based on a statistically significant difference between the experimental and the control conditions. Should all three doses be found to be significantly superior to the control condition, the dose that shows the largest effect size will be considered for the R33 phase. Among doses with similar or same effect size the one that requires the fewer number of weeks will be selected.

[figure not shown]

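### Does sizing R61 at d = .65, presented as a step down from a pilot d of 0.73, leave the trial underpowered?

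*Combined protocol and SAP*

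**What the plan says.** Section C.7 names the R61 primary outcome as the decrease from baseline in PINES activity, regulate versus look, in CRD compared with CD at weeks 2, 4 and 6. It cites the preparatory study, "we obtained a strong effect size of d = 0.73 for 5 days of training", and continues "We will, however, power the current study at a more moderate power of d", giving the value .65. With two-tailed alpha 0.05 and power 0.80 it arrives at 39 per group. It adds: "A significant effect at any dose will meet milestone criteria".

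The pilot is described in C.1.3.3: "BPD subjects (N=19), and healthy volunteers (HC; N=18) performed a cognitive reappraisal-by-distancing task 5 times". The PINES result there is a fall in the BPD group "relative to pretraining, with a large effect size (d=0.73, p<0.03, one-tailed; see Fig. 8". Section A.2 reports what appears to be the same result as "to reduce activity (p=0.03, one-tailed) in the picture induced negative emotion signature (PINES) network".

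Sections C.6.3 and C.6.4 define the R61 analysis. Each participant's regulate-minus-look contrast at weeks 2, 4 and 6 is taken against week 0, and the arms are compared by two-sample t-tests. C.2.6.2 says the control was chosen to be neutral in its effects, although its participants also receive focused practice. C.8 allows that CD may have active features.

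**The concern.** C.7 reads as if R61 has 80% power for an effect somewhat smaller than one already observed. But the observed effect had no BPD comparison arm: every BPD patient in the pilot was trained in distancing, and the only other group was healthy volunteers doing the same task. A pre-post d in one group equals the between-arm d only if (a) the control arm does not change and (b) the d was formed by dividing by the SD of change. C.7 states neither condition.

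Two details add to the doubt. The p value is given as equal to 0.03 in A.2 and as below 0.03 in C.1.3.3. And C.2.2 sets 0.73 beside a much smaller behavioural effect that it also calls significant ("PINES activity was large (d =0.73), while the effect on behavioral ratings of negative valence, though significant, was small (d=0.15"), which raises the question of how the d values were scaled.

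The PINES comparison alone decides whether R33 goes ahead. If .65 were optimistic, a missed milestone could reflect a small sample rather than an ineffective treatment.

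**Working it through.** **Inputs.** From C.7: d = .65, two-tailed alpha 0.05, power 0.80, 39 per group, pilot d = 0.73. From C.4.2.1: 49 recruited per group, 20% loss. From C.1.3.3: 19 BPD patients in the pilot. Not given in the readable text: the standardiser of 0.73, the number analysed, and the expected CD change.

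**1. The plan's own figures.** For a two-sample t-test (noncentral t, 76 df at 39 per group), d = .65 requires n = 38.14, rounded up to 39. Power is 0.809 at 39 per group and 0.799 at 38. Recruitment: 39 / 0.80 = 48.75, rounded up to 49. Both stated figures reproduce. The effect detectable with 80% power at 39 per group is d = 0.643.

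**2. If 0.73 is mean change / SD of change.** Take the between-arm d as 0.73 minus the CD change in SD units, with equal SDs of change in the two arms. The CD values are an assumed range.

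| CD change (SD) | Between-arm d | Per-dose power, 39 per group |
|---|---|---|
| 0 | 0.73 | 0.89 |
| 0.08 | 0.65 | 0.81 |
| 0.10 | 0.63 | 0.78 |
| 0.20 | 0.53 | 0.64 |
| 0.30 | 0.43 | 0.47 |

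The margin before per-dose power falls below 80% is 0.73 − 0.643 = 0.087 SD, or 12% of 0.73.

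**3. If 0.73 was scaled to the SD at a single session.** Then change-scale d = 0.73 / √(2(1 − r)), where r is the between-session correlation (assumed range). With no CD change:

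| r | Change-scale d | Per-dose power |
|---|---|---|
| 0 | 0.52 | 0.61 |
| 0.37 | 0.65 | 0.81 |
| 0.5 | 0.73 | 0.89 |
| 0.7 | 0.94 | 0.98 |

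So .65 may lie below or above the pilot value on the scale that matters.

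**4. What the p value can settle.** For a paired test, t = d√n. With all 19 analysed, d = 0.73 gives t = 3.18 and one-tailed p = 0.0026, which agrees with p below 0.03 but not with p equal to 0.03. Read backwards, p exactly 0.03 gives t = 2.007 and d = 2.007 / √19 = 0.46. That result depends on the number analysed: the same p implies 0.53 at n = 15, 0.61 at n = 12 and 0.73 at n = 9. It is too loose to fix the pilot value.

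**5. Power for the milestone.** Any one dose is enough. Simulating three correlated comparisons with equal effects at all doses, significance in favour of CRD, and between-dose correlation from 0.9 down to 0.3 (assumed):

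| d | Any-dose power |
|---|---|
| 0.46 | 0.63–0.82 |
| .65 | 0.88–0.97 |
| 0.73 | 0.94–0.99 |

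At two sessions a week, the three doses are 4, 8 and 12 sessions, against five in the pilot.

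**The case for a change.** The strongest case for a change is that C.7 presents .65 as a discount without showing that it is one. Even on the most direct reading the margin for control-arm improvement is only about 0.09 SD, and CD patients get matched sessions with practice and shaping. A reader of a missed milestone would want to know what control change had been allowed for. This much stands: the comparison of .65 with 0.73 is loose, and C.7 does not say what CD change it assumes.

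The rest is weaker. The two p values differ only by an equals sign against a less-than sign, which may be loose notation. The behavioural comparison assumes that the d of 0.15 and the significance statement in C.1.3.3 ("the total negative valence ratings for RNeg and LNeg showed a significant decrease post-training (p< 0.05, twotailed") come from one paired test on one measure. That p value is for the two negative-picture conditions combined, and the test used is not stated. Figs 7 and 8, cited for these results, could not be read in the copy reviewed and may give the missing detail.

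There is also support for a small CD change. The outcome is regulate minus look, so retest effects shared by both conditions cancel. CD was chosen for neutrality. And C.1.3.2 reports that, among the groups studied, only healthy volunteers habituated to repeated aversive pictures on their ratings.

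**Conclusion.** The observation is right, but it calls for no change. The pilot d is a single-group pre-post effect and R61 estimates a between-arm difference in change, so describing .65 as more moderate than 0.73 is not a like-for-like comparison. However, the sample size rests on .65, stated with its alpha, sidedness and power, and for that effect the design delivers what it claims: power 0.81 per dose at 39 per group.

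Nothing in the documents shows .65 to be too large. With no CD change and 0.73 on the SD-of-change scale, it is a true discount (power 0.89 at 0.73). On less favourable assumptions per-dose power drops, for example to 0.64 with a CD improvement of 0.20 SD. The any-dose rule softens this for the decision that matters, given equal effects across doses and correlations of 0.3 to 0.9.

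This is a gap in the justification of an assumption, not an arithmetic error. Naming the standardiser, the number analysed and the assumed CD change would make C.7 easier to read. It would leave enrolment, the analysis, the milestone rule and the results as they are. A statistician interpreting R61 will in any case use the observed between-arm difference and its confidence interval, which do not depend on the pilot.
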